## Note:

1) Although not included in the above objectives and endpoints, the efficacy and safety at OPW24 (Week 24 of study intervention treatment) and OPW48 (the last dose of study intervention) in the optional cohort will be evaluated as additional analysis in the similar manner with efficacy and safety at Week 24 and Week 48.

2) Group A= Treatment group consisting of BDQ + CAM + EB

3) Group B= Treatment group consisting of rifamycin (RFP or RBT) + CAM + EB

Key: AEs=adverse event; *atpE*=ATP synthase subunit c; BDQ=bedaquiline; CAM=clarithromycin; CT=computed tomography; EB=ethambutol; ECG=electrocardiogram; MAC=*Mycobacterium avium* complex; MAC-LD=MAC lung disease; MGIT=mycobacterium growth indicator tube; MIC=minimal inhibitory concentration; *mmpT5*=mycobacterial membrane protein transporter-5; NTM=nontuberculous mycobacterial; OPW=week in optional cohort; PD=pharmacodynamics; PK=pharmacokinetics; QOL-B=Quality of Life-Bronchiectasis; RBT=rifabutin; RFP=rifampicin; SoA=schedule of activities; SGRQ= St. George's Respiratory Questionnaire.

## Hypothesis

The hypothesis of this study is that BDQ -containing regimen is superior to rifamycin-containing regimen and increases the proportion of participants with sputum culture conversion in mycobacteria growth indicator tube (MGIT) at Week 24 as compared to rifamycin-containing regimen.

## OVERALL DESIGN

This is a multicenter, randomized, open-label, active-controlled study to evaluate efficacy and safety of BDQ compared with rifamycin administered as part of a treatment regimen with clarithromycin (CAM) and ethambutol (EB) for 48 weeks in adult participants with treatment-refractory MAC-LD. The study will consist of a screening period of 70 days (10 weeks) (including rifamycin washout period of 14 days for participants to whom this is applicable), an open-label treatment period of 48 weeks (baseline visit [Day 1] to Week 48) in Group A or 60 weeks (Day 1 to Week 60) in Group B, and follow-up period of 12 weeks in Group A. Participants will return for study visits biweekly in the first 12 weeks, and then every 4 weeks until Week 60. In addition, this study provides an option to receive BDQ-containing regimen for non-converters in Group B based on the result of microbiological test up to Week 24 as the optional cohort. OPW-2 in optional cohort will be initiation of 2-week washout period in optional cohort.

An Independent Data Monitoring Committee (IDMC) will be commissioned for this study.

A futility analysis will be implemented to evaluate early the benefit/risk balance by assessing safety and efficacy in the first 60 participants (about 30 participants from both groups) who reach the Week-24 time point or discontinued earlier or switched to individualized treatment regimen. This futility analysis is nonbinding and the IDMC will recommend the continuation or termination of the study based on the whole package of information, which also includes other efficacy and safety assessments. Sponsor will decide the continuation or termination of the study based on the recommendation by IDMC.

## NUMBER OF PARTICIPANTS

A target of 124 participants with treatment-refractory MAC-LD will be enrolled in this study.

## TREATMENT GROUPS AND DURATION

Participants who meet all the eligibility criteria will be randomized in a 1:1 (Treatment Group A [Group A]: Treatment Group B [Group B]) ratio stratified by country:

- Group A: BDQ + CAM + EB
- Group B: rifamycin (rifampicin [RFP] or rifabutin [RBT]) + CAM + EB

## EFFICACY EVALUATIONS

Microbiology assessments (MAC-LD Treatment Outcome), clinical assessments in MAC-LD, percentage of participants who undergo a change in their MAC-LD treatment regimen, and a lung function assessment using a spirometry test, will be performed in this study.

## PHARMACOKINETIC EVALUATIONS

Pharmacokinetic (PK) assessments for BDQ (and its active metabolite M2 [optional]) will be based on sparse sampling and will be performed using a Bayesian PK approach. A validated population PK model for BDQ and M2 has been developed that allows estimation of the main PK parameters (maximum plasma concentration [ $C_{max}$ ], area under plasma concentration time curve [AUC], and minimum plasma concentration between 0 hour and the dosing interval  $\tau$  [ $C_{trough}$ ]) based on sparse samples drawn on various study visits. The plasma concentration of CAM and its active metabolite 4-OH CAM will be determined predose and around peak via predose and postdose blood sampling.

## SAFETY EVALUATIONS

Safety assessments will include all adverse events (AEs), physical examination, measurement of body weight, visual examination and audiology, vital signs, electrocardiograms (ECGs), and clinical laboratory tests.

## STATISTICAL METHODS

Statistical analysis will be done by the sponsor or under the authority of the sponsor. A sample size of 124 participants (62 in Group A: the BDQ containing regimen, 62 in Group B: the rifamycin-containing regimen) will have a power of about 80% to show superiority for a 20% difference in proportion of participants having sputum conversion at Week 24 based on a chi-square test (at the 5% 2-sided significance level) on the intent-to-treat (ITT) population.

All efficacy and safety data will be summarized by treatment groups (Groups A and B). For the Group B, data from optional cohort will be analyzed separately.

The Cochran-Mantel-Haenszel test stratified by region (Japan, non-Japan) at the 5% 2-sided significance level will be used to compare sputum culture conversion rate in MGIT at Week 24. A generalized linear model including treatment, region (Japan, non-Japan), time, and treatment-by-time interaction as fixed effects will be applied for the number of sputum culture negative participants and the number of all participants at each timepoint and comparison between treatment groups will be performed using the appropriate contrast for the percentage of negative participants at Week 24. Kaplan Meier estimates will be generated for the time to sputum culture conversion up to Week 24 and Week 48. The changes from baseline in total score of St. George's Respiratory Questionnaire (SGRQ) and respective domain scores will be summarized descriptively at Weeks 24, 48, and 60.

[figure not shown]
For each AE, the percentage of participants who experience at least 1 occurrence of the given event will be summarized by treatment group. Descriptive statistics will be calculated for each laboratory analyte at baseline and for observed values and changes from baseline at each scheduled time point. Changes from baseline results will be presented in pre- versus postintervention cross-tabulations (with classes for below, within, and above normal ranges). Frequency tabulations of the laboratory abnormalities will be made. The effects on cardiovascular variables will be evaluated by means of descriptive statistics and frequency tabulations. Electrocardiogram data will be summarized by ECG parameter. Descriptive statistics will be calculated at baseline and for observed values and changes from baseline at each scheduled time point. Frequency tabulations of the abnormalities will be made. Vital signs including temperature (axillary), heart rate, respiratory rate, oxygen saturation, and blood pressure (systolic and diastolic) values and their changes from baseline, including percentage of participants with values beyond clinically important limits will be summarized. Physical examination findings, visual acuity, color discrimination, visual field, funduscopy, and audiometry data will also be descriptively presented.

The pharmacokinetic/pharmacodynamic (PK/PD) analyses may be performed at earlier time points as necessary to support efficacy and safety findings. If there is any visual trend in graphical analysis, suitable models will be applied to describe the PK/PD relationships. For each intervention group, descriptive statistics, including arithmetic mean, SD, coefficient of variation, median, minimum, and maximum will be calculated for all individual derived PK parameters including exposure information of BDQ and M2 (if applicable) for Group A, and will be calculated for predose and 2 to 4 hours postdose plasma concentrations on Day 1, Weeks 2, 8, 12, 24, and 48 of BDQ, and CAM and 4-OH CAM for both Groups A and B.

The Statistical Analysis Plan (SAP) will describe the planned interim (futility) analyses in detail. Details of the futility analysis (including classification of lack of efficacy) and criterion will be included in the IDMC charter and SAP.

## 1.2. Schema

Figure 1: Schematic Overview of the Study

Key: BDQ=bedaquiline; CAM=clarithromycin; CT=computed tomography; EB=ethambutol; IDMC=Independent Data Monitoring Committee; MAC=*Mycobacterium avium* complex; MAC-LD=MAC lung disease; max=maximum; OPW=week in optional cohort; RBT=rifabutin; RFP= rifampicin; W=Week; W/O=washout

Note:

- 1) OPW-2 - Initiation of 2-week washout period in optional cohort
- 2) OPD1 - Date of starting dose in optional cohort
- 3) OPW24 - Week 24 in optional cohort
- 4) OPW48 - Week 48 in optional cohort

- a Prior to Week 24, participants who are judged to have difficulty continuing their designated treatment regimen due to failure to respond (based on non-conversion and clinical worsening) or the occurrence of AE will be considered treatment failures and can switch to an individualized treatment regimen (see Section 6.8.1), at the discretion of the investigator in consultation with IDMC.
- b After Week 24 assessment, all participants who are judged to have difficulty continuing their designated treatment regimen due to failure to respond (based on non-conversion and clinical worsening) or the occurrence of AE will be considered treatment failures and will be given the option to switch to an individualized treatment regimen (see Section 6.8.1) at the discretion of the investigator.
- c After completion of 48-week treatment, converters who achieved culture conversion at Week 48 in the Group A will be followed for 12 weeks as drug-free period. Participants who failed to achieve sputum culture conversion (non-converters) by Week 48 and continue chemotherapy will be discontinued from the study and switched to another treatment regimen.
- d At Week 24, non-converters in the Group B, will be considered to switch to BDQ-containing regimen at the discretion of the investigators. When the investigator changes to BDQ-containing regimen, 2-week washout of used rifamycin is required before initiation of BDQ-containing regimen.
- e All participants who are judged to have difficulty continuing their BDQ-containing regimen due to failure to respond (based on non-conversion and clinical worsening) or the occurrence of AE will be considered treatment failures and will be given the option to switch to an individualized treatment regimen (see Section 6.8.1) at the discretion of the investigators.

## 1.3. Schedule of Activities (SoA)

	Screening a	Investigation b																Follow-up (Group A)/ Investigation (Group B)			Early discontinuation/ Switch to ITR f
Day (D)/Week (W)	-W10 to D0	Baseline D1 c	W2	W4	W6	W8	W10	W12	W16 d	W20 d	W24 d	W28 d	W32 d	W36 d	W40 d	W44 d	W48 d,e	W52 d	W56 d	W60 d	
Study day	-70 to 0	1	15±2	29±2	43±2	57±2	71±2	85±2	113±3	141±3	169±3	197±4	225±4	253±4	281±4	309±4	337±4	365±4	393±4	421±4	before W60
Screening/administrative																					
Informed consent g	X																				
Inclusion/exclusion criteria h	X	X																			
Medical history and demographics i	X																				
Prestudy therapy	X																				
Pregnancy test (WOCBP only) j	X	X						X			X			X			X			X	X
FSH test k	X																				
HIV infection status	X																				
Hepatitis B and C	X																				
Study intervention/administration																					
Randomization		X																			
Dispense/administer study intervention l		Timing will be at prespecified intervals, as described in the clinical trial protocol.																			
Study intervention accountability 		X	X	X	X	X	X	X	X	X	X	X	X	X	X	X	X	X 	X 	X 	X
Concomitant therapy		Continuously																			
Microbiological assessment																					
Sputum collection m for	X	X	X	X	X	X	X	X	X	X	X	X	X	X	X	X	X	X	X	X	(X)
• Identification and speciation n	X	X	X	X	X	X	X	X	X	X	X	X	X	X	X	X	X	X	X	X	(X)
• MGIT o , agar media	X	X	X	X	X	X	X	X	X	X	X	X	X	X	X	X	X	X	X	X	(X)
• Drug susceptibility testing p	X	X	The testing will be performed on positive isolates at Week 24 as well as the last culture positive isolates in case of participants with non-conversion and recurrence (relapse/reinfection). In addition, it will be performed on positive isolates at early discontinuation (if available).																		
• VNTR or WGS q	X	In case of recurrence (relapse/reinfection), and if acquired resistance (at least 4-fold increased MIC) to BDQ is observed, VNTR and/or WGS will be performed on both baseline and postbaseline isolates.																			
Clinical assessment																					
SGRQ, QOL-B NTM module		X								X							X			X	(X)
Lung function test		X r								X							X			X	(X)
Chest CT s	X									X							X			X	(X)
Pharmacokinetics (PK)																					
Blood sampling for PK of BDQ (Group A)		X u	X u	X t	X t	X u		X u	X t		X u		X t				X u				
Blood sampling for PK of CAM		X u	X u			X u		X u			X u										
Safety assessment																					
Adverse events		Continuously																			
12-lead ECG v	X	X	X	X	X	X	X	X	X	X	X	X	X	X	X	X	X	X	X	X	X
Physical examinations, vital signs w	X	X	X	X	X	X	X	X	X	X	X	X	X	X	X	X	X	X	X	X	X
Clinical laboratory tests x	X	X		X		X		X			X			X			X			X	X

	Screening a	Investigation b																Follow-up (Group A)/ Investigation (Group B)			Early discontinuation/ Switch to ITR f
Day (D)/Week (W)	-W10 to D0	Baseline D1 c	W2	W4	W6	W8	W10	W12	W16 d	W20 d	W24 d	W28 d	W32 d	W36 d	W40 d	W44 d	W48 d,e	W52 d	W56 d	W60 d	
Study day	-70 to 0	1	15±2	29±2	43±2	57±2	71±2	85±2	113±3	141±3	169±3	197±4	225±4	253±4	281±4	309±4	337±4	365±4	393±4	421±4	before W60
Audiology, visual examinations y		X		X cc		X cc		X			X			X			X			X	(X)
Fundoscopy dd		X									X						X			X	(X)

Note: (X)=If available

Key: CAM=clarithromycin; CT=computed tomography; D=day; ECG=electrocardiogram; FSH=follicle-stimulating hormone; HIV= human immunodeficiency virus, ITR=Individualized treatment regimen; MGIT=mycobacterium growth indicator tube; MIC= minimal inhibitory concentration; NTM=nontuberculous mycobacterial; PK=pharmacokinetics; QOL-B=Quality of Life-Bronchiectasis; SGRQ= St. George's Respiratory Questionnaire; SoA=schedule of activities; VNTR: variable number tandem repeat, W=week; WGS: whole genome sequencing; WOCBP: woman of childbearing potential.

## 1.3.1. Schedule of Activities (SoA) in the Optional Cohort

	Washout 	Optional Investigation																
Day (D)/Week (W)	from OPW-2	Baseline (OPD1) aa	OPW2	OPW4	OPW6	OPW8	OPW10	OPW12	OPW16 d	OPW20 d	OPW24 d	OPW28 d	OPW32 d	OPW36 d	OPW40 d	OPW44 d	OPW48 d,bb	Early discontinuation/ Switch to ITR f before OPW48
Study day (optional cohort)	-14 to 0	1	15±2	29±2	43±2	57±2	71±2	85±2	113±3	141±3	169±3	197±4	225±4	253±4	281±4	309±4	337±4	
Washout																		
Washout of rifamycin	X																	
Study intervention/administration																		
Dispense/administer study intervention		Timing will be at prespecified intervals, as described in the clinical trial protocol.																
Study intervention accountability	X	X	X	X	X	X	X	X	X	X	X	X	X	X	X	X	X	X
Concomitant therapy	Continuously																	
Microbiological assessment																		
Sputum collection m for		 cc	X	X	X	X	X	X	X	X	X	X	X	X	X	X	X	(X)
• Identification and speciation n		 cc	X	X	X	X	X	X	X	X	X	X	X	X	X	X	X	(X)
• MGIT o , agar media		 cc	X	X	X	X	X	X	X	X	X	X	X	X	X	X	X	(X)
• Drug susceptibility testing p		 cc	The testing will be performed on the last culture positive isolates in case of participants with non-conversion and recurrence (relapse/reinfection). In addition, it will be performed on positive isolates at early discontinuation (if available).															
• VNTR or WGS q	In case of recurrence (relapse/reinfection), and if acquired resistance (at least 4-fold increased MIC) to BDQ is observed, VNTR and/or WGS will be performed on both baseline and postbaseline isolates.																	
Clinical assessment																		
SGRQ, QOL-B NTM module		 cc									X						X	(X)
Lung function test		 cc									X						X	(X)
Chest CT		 cc									X						X	(X)
Safety assessment																		
Adverse events	Continuously																	
12-lead ECG v		 cc	X	X	X	X	X	X	X	X	X	X	X	X	X	X	X	X
Physical examinations, vital signs w		 cc	X	X	X	X	X	X	X	X	X	X	X	X	X	X	X	X
Clinical laboratory tests x		 cc		X		X		X			X			X			X	X
Pregnancy test (WOCBP only)		 cc						X			X			X			X	X
Audiology, visual examinations y		 cc		X ee		X ee		X			X			X			X	(X)
Fundoscopy dd		 cc									X						X	(X)

Note: (X)=If available, ☒=In principle, no additional test is required as OPD1 as data of Week 24 will be used as the baseline

Key: CAM=clarithromycin; CT=computed tomography; D=day; DST=drug susceptibility testing; ECG=electrocardiogram; FSH=follicle stimulating hormone; ITR=Individualized treatment regimen; MAC=*Mycobacterium avium* complex; MAC-LD=MAC lung disease; MALDI-TOF MS= Matrix-Assisted Laser Desorption/Ionization-Time Of Flight mass spectrometry; MGIT=mycobacterium growth indicator tube; MIC=minimal inhibitory concentration; NTM=nontuberculous mycobacterial; OPD=day in optional cohort; OPW=week in optional cohort; QOL-B=Quality of Life-Bronchiectasis; QTcF=QT corrected according to Fridericia's formula; SGRQ= St. George's Respiratory Questionnaire; SoA=schedule of activities; VNTR: variable number tandem repeat, W=week; WGS: whole genome sequencing; WOCBP: woman of childbearing potential.

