- w. Examination of height (screening only), body weight measurement, observation for skin events/reactions, assessments performed as part of the clinical course of NTM related disease (body temperature, heart rate, respiratory rate, and oxygen saturation) and additional assessments (systolic blood pressure and diastolic blood pressure). Physical examination and vital signs will be performed before intake of study intervention and blood sampling.
- x. Including hematology, chemistry and urinalysis.
- y. Including visual acuity, color discrimination, visual field. Audiology and visual examinations within 4 week prior to Day 1 and within 4 days prior or after each visit other than Day 1 will be acceptable.
- z. After Week 24 assessment, all participants in the Group B who are non-conversion and well-tolerated, will be considered to receive the BDQ-containing regimen at the discretion of the investigators. When the investigator changes to BDQ-containing regimen, 2-week washout of treated rifamycin must be given before initiation of BDQ-containing regimen. The investigators can postpone the decision to transfer

to the optional cohort for up to Week 32 in order to confirm a sputum culture positive at Week 24, if necessary. If decision to transfer to the optional cohort exceeds Week 32 for reasons such as time required to obtain the result of microbiology assessment of Week 24, the period may be extended. If necessary, consider study date of OPD1 by adding the number of days required to switch to the optional cohort to study date of Week 24.

- aa. OPD1 is Day 1 for participants who are transferred to optional cohort. Assessments planned on OPD1 must be performed prior to first dose of BDQ. The investigators can postpone the decision to switch to the optional cohort for up to Week 32 in order to confirm sputum culture positive at Week 24. If decision to transfer to the optional cohort exceeds Week 32 for reasons such as time required to obtain the result of microbiology assessment of Week 24, the period may be extended.
- bb. Upon completion of the 48-week optional treatment period, the observation of each participant will be completed.

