- cc. In principle, testing data at Week 24 will be used as that of OPD1, so it is not necessary to perform another test as OPD1. If the transition period is extended due to confirmation of the result of sputum culture, the result of microbiology assessment of Week 24 will be used as that of OPD1, the latest data (Week 28, etc) will be used when specified testing other than the microbiology assessment have been performed after Week 24 in Group B.
- dd. Fundoscopy within 4 week prior to Day 1 and within 4 days prior or after each visit other than Day 1 will be acceptable.
- ee. Audiology must be done only in subjects who are taking aminoglycoside

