## 6.8. Concomitant Therapy

Concomitant therapies administered after signing informed consent (70 days before first dose of study intervention, including the extension period if screening period is extended) and prestudy therapies for pulmonary MAC disease administered prior to signing informed consent must be recorded at screening.

Concomitant therapies must be recorded throughout the study from signing of the ICF up to the last study visit. Concomitant therapies should also be recorded beyond the last follow-up visit only in conjunction with new or worsening AEs and SAEs that meet the criteria outlined in Serious

Adverse Events in Section 8.3.1, Time Period and Frequency for Collecting Adverse Event and Serious Adverse Event Information.

All therapies (prescription or over-the-counter medications, including vaccines, vitamins, herbal supplements; nonpharmacologic therapies such as electrical stimulation, acupuncture, special diets, exercise regimens, or other specific categories of interest) different from the study intervention must be recorded in the Concomitant Therapy Section of the eCRF. Recorded information will include a description of the type of therapy, duration of use, dosing regimen, route of administration, and indication. For any concomitant therapy given as a treatment for a new condition or worsening of an existing condition, the condition must be documented in the Adverse Event Section of the eCRF. Modification of an effective preexisting therapy should not be made for the explicit purpose of entering a participant into the study.

It is important to record the use of biotin because of its potential to affect certain laboratory assays when high levels of biotin are present in serum/plasma samples, leading to incorrect test results for certain laboratory parameters. All prior and concomitant treatment with MAC-LD drugs will be recorded. For participants who were previously diagnosed with MAC-LD and are being treated or will start treatment at screening, the start date and details of their treatment regimen must be recorded. Participants who are taking rifamycin before start of the study intervention will be required to discontinue rifamycin to allow for a minimum 14-day washout period (to avoid DDIs between rifamycins and BDQ). Participants who are transferred to the optional cohort will be required to discontinue rifamycin to allow for a minimum 14-day washout period before start of the BDQ-containing regimen.

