## 7. DISCONTINUATION OF STUDY INTERVENTION AND PARTICIPANT DISCONTINUATION/WITHDRAWAL

### 7.1. Discontinuation of Study Intervention

A participant's study intervention must be discontinued if:

- The participant withdraws consent to receive study intervention.
- The investigator believes that for safety reasons or tolerability reasons (eg, AE) it is in the best interest of the participant to discontinue study intervention.

- The participant has a QTcF prolongation (defined as a QTcF value  $\geq 500$  ms, or an increase from baseline of  $>60$  ms) at any given time point (confirmed by repeat ECGs).
- The participant requires treatment with any of the prohibited medications listed in Section 6.8, [Concomitant Therapy](#).
- The participant becomes pregnant. Refer to Section 10.5, [Appendix 5: Contraceptive Guidance](#).
- Noncompliance with study intervention administration as defined in [Table 3](#).
- The participants discontinued administration of study intervention before Week 48 in Group A, Week 60 in Group B or OPW48 in optional cohort.

If a participant discontinues study intervention before Week 48 in Group A, Week 60 in Group B or OPW48 in the optional cohort, the participant will receive the assessments of early discontinuation or withdrawal.

The early discontinuation visit assessment will be performed within 7 days of the investigator's discretion to discontinue treatment with study intervention, unless the participant withdraws consent. Study intervention assigned to the participant who discontinued study intervention may not be assigned to another participant.

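### The optional-cohort schedule does not clearly require a chemistry or pregnancy test before the first bedaquiline dose; for a Week 32 decision the Week 24 results would be about 10 weeks old

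*Protocol*

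**What the plan says.** **Optional-cohort schedule (Protocol 1.3.1).** The OPD1 cells for clinical laboratory tests and pregnancy test carry a crossed box, which the key explains as "In principle, no additional test is required as OPD1 as data of Week 24 will be used as the baseline". The washout column is blank for both rows.

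**Footnotes to 1.3 and 1.3.1.** Footnote cc, attached to those cells, says of Week 24 data "so it is not necessary to perform another test as OPD1". If the transition is extended, "the latest data (Week 28, etc) will be used when specified testing other than the microbiology assessment have been performed after Week 24". Footnote aa says "Assessments planned on OPD1 must be performed prior to first dose of BDQ". Footnotes z and aa let the decision wait until Week 32, and both then provide for a longer wait: "If decision to transfer to the optional cohort exceeds Week 32".

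**Washout.** Protocol 6.8: "Participants who are transferred to the optional cohort will be required to discontinue rifamycin to allow for a minimum 14-day washout period".

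**Main schedule (Protocol 1.3).** After Week 24, the next chemistry and pregnancy tests in Group B are at Week 36. ECG, examination and vital signs continue at Weeks 28 and 32.

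**Section 7.1.** If study intervention stops early (before Week 60 in Group B), "the participant will receive the assessments of early discontinuation or withdrawal", within 7 days. The schedule column for that visit is headed for early discontinuation or a switch to an individualized regimen. It does not name transfer to the optional cohort.

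**The concern.** A participant about to start 400 mg daily of a new drug would normally have recent electrolytes, liver tests and, where relevant, a pregnancy test. The protocol itself supplies the reasons:

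- It lists hypokalemia and hypomagnesemia as torsades risk factors (exclusion criterion 8).
- It lists AST and ALT increases and liver disorder as frequent with rifampicin, the drug usually being stopped (Section 2.2.1).
- It says BDQ has a liver-injury signal and an average terminal half-life of about 5.5 months (Section 2.2), so a loading phase cannot quickly be undone.
- "The participant becomes pregnant" is a Section 7.1 reason to stop study intervention. Section 6.8.2 requires that no Section 7.1 condition be present at the decision, yet for a Week 32 decision the last scheduled pregnancy test is then 8 weeks old.

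The protocol is firmer in a neighbouring case. A switch to an individualized regimen, even one that only drops ethambutol, must be preceded by a visit (Section 6.8.1, footnote f) at which laboratory and pregnancy tests are marked without condition. A first exposure to BDQ has no equally clear rule.

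**Working it through.** **The plan's own count.** Table 4 gives 9 to 12 chemistry samples per participant. Counting marked cells:

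- Never transferred: screening, Day 1, Weeks 4, 8, 12, 24, 36, 48, 60 = 9.
- Transferred: 6 up to Week 24 (screening, Day 1, Weeks 4, 8, 12, 24) + 6 afterwards (OPW4, 8, 12, 24, 36, 48) = 12.

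Both ends reproduce, and one more draw at transfer would make 6 + 1 + 6 = 13.

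**Inputs.** Study days from Protocol 1.3: Week 24 = 169 (±3), Week 28 = 197, Week 32 = 225 (±4), Week 36 = 253. Washout is 14 days, the minimum. I assume that washout starts on the decision day.

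**Age of Week 24 results at first BDQ dose** = decision day + 14 − 169:

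| Decision | OPD1 day | Age at first dose | Week 24 to OPW4 (chemistry) | Week 24 to OPW12 (pregnancy) |
|---|---|---|---|---|
| Week 24 | 183 | 14 days (2 weeks) | 6 weeks | 14 weeks |
| Week 28 | 211 | 42 days (6 weeks) | 10 weeks | 18 weeks |
| Week 32 | 239 | 70 days (10 weeks) | 14 weeks | 22 weeks |

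The last two columns add 4 and 12 weeks to the age.

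**Visit windows for a Week 32 decision.** Shortest: (221 + 14) − 172 = 63 days. Longest: (229 + 14) − 166 = 77 days. That is 9 to 11 weeks.

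**Extended decision.** The last nominal day before the Week 36 tests is 252. If those tests are not then taken during washout, the age is 252 + 14 − 169 = 97 days (13.9 weeks).

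**At a Week 32 decision itself.** 225 − 169 = 56 days, or 8 weeks.

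**Does footnote cc refresh these results?** Only where a test was actually done after Week 24. That holds for ECG, examination and vital signs, but not for chemistry or pregnancy, which have no scheduled test at Week 28 or 32.

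**The case against.** **Section 7.1 may already require the tests.** This is the strongest point. Rifamycin is a study intervention (Section 2), and a transfer stops it before Week 60. The early-discontinuation visit falls within 7 days, inside the washout, and its chemistry and pregnancy cells are unconditional. Footnote cc does not conflict, because a draw taken then could be its latest data. Section 6.8.2 is judged at the decision, before rifamycin stops, so applying Section 7.1 would not make every switcher ineligible. This reading stands as possible, but the column heading omits transfers and the OPD1 key points the other way. A reader might infer that the protocol definitely requires no test; the documents support only that the requirement is unclear.

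**Table 4.** A reader might take its maximum of 12 as proof that no transfer draw is planned. It is not proof. An optional-cohort participant who switches to an individualized regimen must have a visit with laboratory tests, which already makes 6 + 6 + 1 = 13. The table omits a mandated draw, so its silence decides nothing.

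**Late decisions.** A reader might use the SAP's 42-day MGIT value to argue that late transfers are typical. That is the value assigned to negative cultures (SAP 5.4.2.1), whereas transfer rests on a positive, so it gives only an upper bound on the incubation wait.

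**Comparison with Group A.** Numeric chemistry limits for randomised participants are applied during screening, which may last 10 weeks or, if extended, 15. Footnote c asks that Day 1 assessments generally be performed before dosing, not reported. The first on-treatment tests (Week 4 chemistry, Week 12 pregnancy) match OPW4 and OPW12. The remaining differences are the Day 1 chemistry draw and the required negative Day 1 serum pregnancy test.

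**Routine interval.** Chemistry is 12-weekly from Week 12 in both groups, so a 10-week age lies inside it. The gap to OPW4, decision week − 18, exceeds 12 only for decisions after Week 30. This limits the size of the point, although starting a QT-prolonging drug differs from routine monitoring.

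**Safeguards.** Section 8.2.6 has AST, ALT and bilirubin followed every 2 weeks after an elevation; a triplicate ECG is due at OPW2, and confirmed prolongation prompts electrolyte checks; unscheduled and extra pregnancy tests are allowed; footnote z and Section 6.8.2 screen for tolerability. These are real. But the first needs an elevation already seen, the ECG comes after loading has begun, and the rest leave testing to judgement.

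**Conclusion.** The point holds as a gap in clarity with a safety consequence. Neither the optional-cohort schedule nor any safeguard clearly requires chemistry or a pregnancy test between Week 24 and the first BDQ dose, and whether Section 7.1 fills the gap is not stated. If it does not, the results in hand are 2 to 10 weeks old for decisions from Week 24 to Week 32, and older on the extended route.

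These figures assume nominal visits unless windows are shown, a 14-day washout starting at the decision, and no discretionary test. Prompt transfers are little affected. The pregnancy point concerns only women of childbearing potential, and the number of switchers is not given.

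A reader might also infer that switchers have no QTcF reference for the >60 ms rule. The documents do not support that: footnote aa makes OPD1 their Day 1, and footnote cc and SAP 5.1 supply the value. For a Week 32 decision the latest scheduled ECG is pre-dose. For prompt transfers it is the Week 24 ECG, taken 2 to 4 hours post-dose; the size of any resulting bias is unknown. This is a secondary clarification.

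The Week 24 primary comparison is not affected. The change is worth making because it is cheap and settles the ambiguity.

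**What to change.** - Amend footnote cc, the table key and the washout and OPD1 columns of Section 1.3.1 so that chemistry (electrolytes, AST, ALT, bilirubin) and, for women of childbearing potential, a urine pregnancy test are done during the 2-week washout and reviewed before the first BDQ dose. Week 24 data can still serve for culture, CT, SGRQ and lung function.
- State in Section 7.1 that these tests serve as its assessment for participants transferring to the optional cohort.
- Raise Table 4's chemistry maximum from 12 to 13.
- As a secondary clarification, name in Section 8.2.3 the ECG that is the QTcF reference for switchers.

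**Cost.** Amendment wording, one 2.5 mL sample per switcher and one urine test where applicable, which the protocol already has read locally. A switcher's planned blood volume is 12×2 + 12×2.5 + 7.5 + 2 + 20 = 83.5 mL (including the pregnancy-test samples) and becomes 86.0 mL, below the 115.5 mL limit. Chemistry is run centrally with no stated turnaround, so the sample should be taken early in washout; if results are late, OPD1 may slip by some days.
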